172 1. To investigate whether increases in 24-h EE by cold exposure lead to increased *ad libitum* food
173 intake, as measured using a vending machine paradigm.

174 2. To determine whether the effects of increased EE due to cool temperature exposure on
175 energy intake are only concomitant with the increase in EE or persist until the following day.
176 This will be explored by repeating the cool temperature exposure intervention twice: i) once
177 inside the whole-room calorimeter with an *ad libitum* diet; and, ii) once inside the whole-room
178 calorimeter during a fixed diet, followed by one day of *ad libitum* food intake on the vending
179 machines.

180 **Secondary Aims**

181 1. To determine whether 36 hrs of fasting will result in a change in energy intake on the following
182 day, and to determine whether the decrease in 24-h EE during fasting will correlate with
183 amount of food consumed the following day.

184 2. To determine if cold exposure will alter the 24-h respiratory quotient (RQ, an approximation
185 for the ratio of carbohydrate-to-fat oxidation rates), and test whether the induced RQ changes
186 independently contribute to the altered energy intake.

187 3. To determine if the 24-h EE responses to cool temperature exposure correlate with core body
188 temperature or changes in peripheral skin temperatures, and to determine if these changes
189 are related to body adiposity or associated with food intake.

190 4. To assess if behavioral testing addressing dietary restraint, stress related eating behaviors, and
191 executive function or the responses to visual analogue scales assessing hunger modify any
192 observed EE to energy intake association.

193 5. To assess whether the above behavioral testing as measured by previously validated

194 questionnaires and tasks are associated with measured food intake or hormone

195 concentrations.

196 6. To assess if concentrations of appetitive or exercise-induced hormones will correlate with the

197 observed changes in EE and energy intake.

198 7. To determine if any observed association between EE and energy intake predicts future weight

199 change at 6 months and 1 year.

200 **HYPOTHESES**

201 **Primary Hypotheses**

202 1. An increase in 24-h EE, as induced by 24 hours of exposure to 19°C, will be associated with an

203 increase in *ad libitum* food intake, which will exceed the increase in 24-h EE, on the day of the

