204 intervention and the effect will persist for at least 24 hours.

205 2. The effect of increasing EE by cool temperature exposure on *ad libitum* food intake will be

206 evident both on the day of the intervention and the following day.

207 **Secondary Hypotheses**

208 1. Thirty-six hours of fasting will induce compensatory overeating when the subject is re-

209 introduced to food, and the decrease in 24-h EE during fasting will positively predict the

210 degree of energy consumption.

211 2. The creation of an energy deficit will lead to a decrease in RQ, but the observed changes in

212 energy intake due to changes in EE will be independent of any change in RQ.

213 3. Subjects with less body adiposity will have a greater increase in 24-h EE with cool temperature

214 exposure and a greater decrease in distal skin temperatures while more obese subjects will

215 have a smaller increase in 24-h EE with cool temperature exposure and a greater decrease in

216 proximal skin temperatures indicating greater reliance on insulating mechanisms rather than
217 adaptive thermogenesis.

218 4. Measures of executive function and results of questionnaires related to eating behaviors will
219 be associated with the amount of *ad libitum* caloric intake, but the effects of EE will be
220 independent of these relationships.

221 5. Induced increases in EE will be associated with changes in hormone concentrations, including
222 cold-induced increases in adiponectin, insulin, free T4, TSH, FGF21, glucagon, ghrelin, urinary
223 free cortisol, urinary catecholamines and decreases in leptin, GLP-1, PP and PYY, and at least
224 some of these changes will be associated with the change in food intake.

225 6. The amount of energy intake increase after an increase in EE or the ratio of Δ energy
226 intake/ Δ EE will be directly associated with weight change at 6 months and 1 year.

227 **STUDY DESIGN AND METHODS**

228 **Study Design**

229 This is a inpatient natural history, observational cohort study of healthy human research
230 volunteers with research interventions designed to understand the relationship between the
231 physiologic sensing of EE and food intake behavior. This is primarily a cross-sectional study but with a
232 longitudinal component to assess the association of baseline measurements with future weight
233 change.

234 **Subjects**

235 Sixty-eight healthy participants of all body sizes representing both genders, without evidence

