673 baseline admission. This sample size will provide 80% power ($\alpha=0.005$) to detect a simple

674 correlation of 0.5 between change in EE due to any intervention and change in energy intake. The

675 alpha level for this interim analysis is set to 0.005 based on the alpha spending function approach

676 [[64, 65]]. The alpha level for the final analysis will remain at 0.01. More importantly, the interim

677 analysis will allow us to assess whether there is likely to be a significant correlation once the full

678 sample size is reached or whether the null hypothesis is highly likely to be accepted. If the correlation

679 within the first 47 subjects is <0.2 , the study will be stopped as the null hypothesis will be highly likely

680 to be accepted. However, if the correlation is much stronger than anticipated, the study will continue

681 to obtain adequate sample size for adjusting for covariates and answering the secondary research

682 questions. If the interim correlation is between 0.2 and 0.4, the final sample size will be increased

683 from 68 to 124 subjects to provide 80% power at an alpha of 0.01 to detect a more moderate

684 association. Achieved power as a function of final sample size, alpha and correlation value between

685 change in EE and energy intake is reported in Table 3. Assuming a 30% dropout rate, we will ask for a

686 total enrollment of 160 subjects.

687

688 **Table 3. Power calculations based on different values of alpha (α), correlation value (r) and**
 689 **sample size (n).**

α	r	n	Power
0.001	0.30	47	0.103
		68	0.208
		124	0.544
	0.40	47	0.308
		68	0.547
		124	0.915
	0.50	47	0.635
		68	0.873
		124	0.997
0.005	0.30	47	0.223
		68	0.378
		124	0.727
	0.40	47	0.503
		68	0.732
		124	0.969
	0.50	47	0.803*
		68	0.949
		124	0.999
0.01	0.30	47	0.301
		68	0.470
		124	0.799
	0.40	47	0.598
		68	0.804**
		124	0.982
	0.50	47	0.863
		68	0.969
		124	1.000

690 *: interim analysis

691 **: final analysis

692
 693 **Data Analysis**

694 Our primary outcome will be the association between the change in EE and the change in
 695 energy intake induced by the interventions (cool temperature exposure and fasting). As the purpose
 696 of this protocol is to evaluate the effects of altered EE on food intake regardless of the type of
 697 intervention, only within-subject analyses rather than between-interventions analyses will be carried

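### The primary outcome and the n=47 stop rule take in fasting as well as cold and do not say which EE–intake correlation governs, although the primary aims concern cold exposure only

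*Combined protocol and SAP*

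**What the plan says.** **Aims and hypotheses.** Primary Aim 1 is "To investigate whether increases in 24-h EE by cold exposure lead to increased" food intake. Primary Aim 2 and both Primary Hypotheses are also about cool temperature. Fasting appears as Secondary Aim 1 and Secondary Hypothesis 1. The latter expects compensatory overeating when the subject is "introduced to food, and the decrease in 24-h EE during fasting will positively predict the" amount eaten.

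**Data Analysis.** The primary outcome is the association between the change in EE and the change in "energy intake induced by the interventions (cool temperature exposure and fasting"). The reason given is that the purpose "of this protocol is to evaluate the effects of altered EE on food intake regardless of the type of" intervention. Table 4 agrees with this wider scope: its primary-outcome rows include EE on Day 21 (the fasting chamber) and intake on Day 22 (the day after the fast).

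**Sample Size Calculation.** The interim look is powered for a "correlation of 0.5 between change in EE due to any intervention and change in energy intake". If the correlation "within the first 47 subjects is" below 0.2, "the study will be stopped as the null hypothesis will be highly likely" to be accepted. Between 0.2 and 0.4 the final sample grows from 68 to 124. The text speaks of the correlation in the singular and does not identify it.

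**The concern.** Each subject can supply at least three pairs of changes: cold with intake the next day (Days 14 and 15), cold with intake in the chamber the same day (Day 18), and fasting with intake the next day (Days 21 and 22). A rule written as mandatory depends on one unnamed correlation, and the candidates are not expected to behave alike.

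The plan expects cold to raise EE (the Introduction cites about 5 to 15%) and to raise intake. It expects fasting to raise intake while EE falls. The mean shifts therefore run in opposite directions for fasting and in the same direction for cold. If the fasting hypothesis means that a larger drop predicts more eating, the correlation within fasting is also negative on the signed EE change.

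The threshold of 0.2 is signed as written. Depending on which correlation is used, the study could stop, or nearly double, for reasons that have little to do with the cold-exposure question it was set up to answer.

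**Working it through.** **1. The plan's own power figures.** Inputs from the Sample Size Calculation section and Table 3: n=47, r=0.5, two-sided alpha 0.005 (interim); n=68, r=0.4, alpha 0.01 (final). By Fisher z, power = Φ(atanh(r)·√(n−3) − z):

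- Interim: 0.5493 × 6.633 − 2.807 = 0.837, giving 0.799.
- Final: 0.4236 × 8.062 − 2.576 = 0.840, giving 0.799 to 0.800.

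The exact calculation under a bivariate normal gives 0.803 and 0.804, as stated, and reproduces all 27 cells of Table 3. These figures assume one pair of changes per subject.

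**2. Chance of meeting the stop rule for one correlation, one pair per subject, n=47.** P(r<0.2) = Φ[(atanh 0.2 − atanh ρ)·√44].

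- Cold alone, ρ=+0.4: (0.2027 − 0.4236) × 6.633 = −1.465, giving 7.1%.
- Fasting alone, ρ=−0.4: (0.2027 + 0.4236) × 6.633 = 4.155, giving about 100%.
- Other true values: 1.1% at 0.5, 2.5% at 0.46, 23.9% at 0.3, 91.1% at 0.

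**3. One pooled correlation (illustration only).** The documents give no standard deviations (SDs) of the changes and no EE change under fasting, so both are assumed. Take unit SDs, one cold and one fasting pair per subject, and a cold correlation of 0.4. Let dx and dy be the cold-minus-fasting differences in mean EE change and mean intake change, in SD units. Then

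pooled r = [(r_cold + r_fast)/2 + dx·dy/4] / √[(1 + dx²/4)(1 + dy²/4)].

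Example with r_fast=+0.4, dx=2, dy=−0.5: (0.40 − 0.25)/√(2 × 1.0625) = 0.15/1.458 = 0.10.

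The stop probabilities come from simulating 47 subjects, with pairs treated as independent, 1,000 runs per case.

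| r_fast | dy | Pooled r at dx = 1, 2, 3 | P(r<0.2) at dx = 1, 2, 3 |
|---|---|---|---|
| +0.4 | +0.5 | 0.46, 0.45, 0.42 | about 0% |
| +0.4 | 0 | 0.36, 0.28, 0.22 | 5%, 20%, 41% |
| +0.4 | −0.5 | 0.24, 0.10, 0.01 | 35%, 85%, 97% |
| −0.4 | +0.5 | 0.11, 0.17, 0.20 | 81%, 59%, 48% |
| −0.4 | 0 | 0.00, 0.00, 0.00 | 96%, 97%, 98% |
| −0.4 | −0.5 | −0.11, −0.17, −0.20 | about 100% |

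With two cold pairs and one fasting pair per subject, the last row becomes +0.02, −0.06 and −0.11, with stop probabilities of 97 to 100%.

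**4. Does adjusting for intervention cure it?** A main effect removes the mean shifts but not opposite slopes. With +0.4 and −0.4, the correlation after centring within each condition is (0.4 − 0.4)/2 = 0.

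**5. Does other text settle the matter?** In the Data Analysis section, intervention type is a fixed effect in the model for determinants of the EE response. Correlations stratified by intervention are written for the hormone analyses. The regression of intake change on EE change lists age, sex, race, aerobic capacity, fat mass, fat-free mass, RQ and a sequence variable, but no intervention term and no interaction.

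**The case against.** A reader might infer that the plan stacks cold and fasting into one coefficient, and that its own hypotheses guarantee opposite signs and so a futility stop. The documents do not support that much.

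- **Pooling is not written.** Changes are calculated separately for each intervention. The analyses are described as within-subject and not between interventions. Cold and fasting EE changes are to be correlated with each other, so they are kept as distinct variables. The power tables fit one pair per subject, whereas pooling would give at least 2 × 47 = 94 pairs at the interim. The phrase about any intervention may mean whichever one is under test.
- **The negative sign within fasting rests on one ambiguous sentence.** Read as the size of the drop, the correlation is negative; read as the signed change, it is positive. Secondary Aim 1 gives no direction.
- **The size of any pooling effect is assumed.** Some rows of the table leave r intact or raise it.
- **A strongly negative r does not fit the rationale of the stop rule**, which is that the null will probably be accepted, and the test is two-sided.

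All four points stand against the stronger reading. They do not identify the governing correlation. If the analyses are separate, the text still does not say whether same-day cold, next-day cold or fasting decides. The last point shows that the sign of the rule also needs stating, because the text as written has the study stop at any value below 0.2. The conflict in mean shifts does not depend on how the fasting sentence is read, though it matters only if the data are pooled.

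**Conclusion.** The concern holds as a conflict within the text and a gap in specification. The primary outcome is wider than the primary aims, and the correlation that decides between stopping, continuing and enlarging the study is not named.

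The firm figures are 7% for the chance of meeting the stop rule with cold alone at a true correlation of 0.4, and about 100% with fasting alone at −0.4. Both assume one pair per subject and bivariate normality, and the second also assumes that the fasting hypothesis refers to the size of the drop. The pooled results show only that r can fall below 0.2 while the cold correlation is as planned. Their size cannot be derived from the documents, and pooling may also preserve or inflate r. It would be wrong to conclude that the plan does pool, or that a futility stop is to be expected. The stated power figures are correct for one pair per subject.

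**What to change.** Before the interim look, amend the Sample Size Calculation and Data Analysis sections and Table 4 as follows.

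- Define the primary outcome, the n=47 rule and the final test on one named cold-exposure correlation, and state its days and comparator. The candidates are Day 18 EE and intake against Day 10, or Day 14 EE against Day 6 paired with Day 15 intake against the baseline vending days (7 to 9). If Day 18 is chosen, settle its EE comparator explicitly: Data Analysis measures EE changes against energy balance (Day 6), while Day 18 intake is compared with Day 10.
- State the sign convention of the 0.2 and 0.4 thresholds.
- Analyse fasting separately under Secondary Aim 1, and say whether the expected correlation with the signed EE change is positive or negative.
- If a combined mixed model is kept, include intervention and an EE-change-by-intervention interaction, account for repeated pairs per subject, and do not base the stop rule on a common slope.

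The cost is wording only: no new data, and no change to the power calculations.

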645 estradiol and progesterone (women only). Urine pregnancy test (β -hcg) will be done in females only.
646 The DXA scan will not be performed if the pregnancy test is positive.

647 **Blood Withdrawal**

648 Blood withdrawal will remain within the NIH guideline of <10.5 mL/kg or <550 mL (whichever
649 is smaller) every 8 weeks for research purposes. The total amount of blood drawn is detailed below.

650

651

Tests	Amount
Screening lab work	32 mL
OGTT	151 mL
Fasting blood measurements	
EBL chamber (pre- and post-)	76 mL
CIT chamber (pre- and post-)	60 mL
FST chamber (pre- and post-)	60 mL
Total (baseline admission):	379 mL
Outpatient visits	
6 months	32 mL
1 year	32 mL
Total:	443 mL

652

653 **Sample Size Calculation**

654 The sample size calculation to answer the primary research question is based on the number
655 of patients needed to demonstrate an association between any change in EE due to interventions and
656 subsequent change in energy intake. In preliminary analyses using data from our clinical research unit
657 [13], the cross-sectional Pearson correlation between unadjusted 24-h EE during energy balance and
658 energy intake is 0.46 ($p<0.0001$). A target sample size of 46 participants will provide a power of
659 greater than 0.80 with an alpha of 0.05 to detect a 0.40 correlation ($r^2=0.16$) using simple linear
660 regression assuming that the association between change in EE and change in energy intake will be
661 the same as that between EE and energy intake. However, any finding will subsequently be adjusted
662 in multivariate linear regression analysis for age, sex, race, fat mass and fat free mass (5 covariates),
663 which requires a minimum of 50 volunteers. In addition, given the number of analyses that will be
664 done, an alpha of 0.01 is likely more appropriate. Therefore, to detect a correlation of 0.4 with a
665 power >0.80 at an alpha = 0.01, a total of 68 subjects will be enrolled for the core study (Table 2).

666

667 **Table 2. Sample size calculations achieving a statistical power ≥ 0.8 .**

	$\alpha=0.05$	$\alpha=0.01$	$\alpha=0.005$	$\alpha=0.001$
r=0.50	n=29	n=41	n=47	n=59
r=0.40	n=46	n=68*	n=77	n=98
r=0.30	n=84	n=124	n=142	n=181

668 r: Pearson's unadjusted correlation between change in EE and change in energy intake

669 α : significance level (2-sided)

670 *: Sample size for the final analysis

671

672 An interim analysis will be conducted when a target sample size of 47 subjects complete the

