698 out to evaluate the EE response to each intervention compared to energy balance. For descriptive
699 statistics, normally distributed variables will be described with means and standard deviations,
700 skewed variables will be described with medians and interquartile range. Baseline differences in
701 demographics between sexes and races will be assessed using Student's *t*-test or one-way ANOVA,
702 respectively. Determinants of the EE response to interventions will be determined using mixed
703 models to account for repeated measures and including the variables age, sex, race, percentage body
704 fat, aerobic capacity and type of intervention as fixed effects. The diagonal (DIAG), the compound-
705 symmetry (CS) and the first-order autoregressive (AR1) covariance structures will be considered for
706 estimation of the random effect of the within-subject repeated measures. The model fit of all
707 calculated models will then be compared using the Bayesian information criterion (BIC) statistic to
708 select the best model in terms of covariance structure for random effects and the number of
709 predictors (i.e., lowest BIC). Post-hoc tests comparing interventions to 24-h EE during energy balance
710 will be conducted using the Dunnett's test to correct for multiple comparisons.

711 The change in 24-h EE during each intervention will be calculated as the absolute change in
712 kcal as well as percent change compared to energy balance. Similarly, change in 24-h RQ,
713 carbohydrate and fat oxidation rates, sleeping EE and sleeping RQ will be also calculated and
714 considered in the analyses. Changes in *ad libitum* food intake due to interventions will be calculated
715 as absolute kcal change as well as percent change in weight maintaining energy needs. Associations
716 between continuous variables will be quantified by Pearson's *r* for data that are normally distributed
717 and Spearman's ρ for data not normally distributed. These analyses will include correlations among
718 changes in 24-h EE during fasting and cool temperature exposure to uncover those EE responses that
719 share common underlying mechanisms, and the association between the EE responses and

720 concomitant and subsequent *ad libitum* food intake. Multivariate regression models will be calculated
721 to control for potential confounders including age, sex, race, aerobic capacity, fat mass and fat free

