771 evaluated and compared by the BIC statistic to identify the best model for weight data over time.
772 Changes in EE after 24-h of fasting and its association with changes in body weight at 6 months and 1
773 year will be combined with data from prior studies (using the exact same methodology) to increase
774 the statistical power of the weight change analysis (currently we have >60 subjects with complete
775 data available at baseline).

776 Statistical analysis will be performed using SAS with E-guide (SAS Institute, Cary, NC). All tests
777 of primary outcome measures will have a 2-sided Type 1 error of $p=0.01$. For the secondary outcome
778 analyses, we will control for Type 1 error at the level of the comparison with $p=0.05$ as each
779 hypothesis is substantively important and stated *a priori*.

780 **Informed Consent Process**

781 Written informed consent will be obtained from the participant prior to any screening visits,
782 study procedures or treatments. The person obtaining consent will explain the study in language
783 understandable to the subject. Sufficient time and opportunity will be given for discussion of the
784 research as well as to answer any questions they may have, taking care to minimize or eliminate the
785 perception of coercion or undue influence. The participant and the investigator will sign the current
786 IRB-approved informed consent document. A copy of the consent will be given to the subject for
787 future reference. The signed documents will be sent to the Medical Records Department for
788 placement in the subject's permanent record.

789 Participants will have the opportunity to carefully review the written consent form, either as a
790 physical or electronic document, and ask questions prior to signing. Participants will be informed that
791 participation is voluntary and that they may withdraw from the study at any time, without prejudice.

792 The consenting process may be performed using the NIH iMedConsent platform (which is 21
793 CFR Part 11 compliant). If the iMedConsent platform is used, then the participant and consenting
794 investigator will review and sign the current IRB-approved electronic informed consent document
795 using a hand signature (e.g., signing using a finger, stylus, or mouse). Electronic signatures (i.e., the
796 “signature” and a timestamp are digitally generated) will not be used. If a paper copy of the IRB-

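### One lowest-BIC comparison picks both the covariance structure and the predictors of the EE response; with the estimation method unstated, REML fitting would make the choice of predictors depend on measurement scale

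*Combined protocol and SAP*

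**What the plan says.** All references are to the combined protocol and SAP.

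- **Predictors.** Data Analysis describes mixed "models to account for repeated measures and including the variables age, sex, race, percentage body" "fat, aerobic capacity and type of intervention as fixed effects. The diagonal (DIAG), the compound"-symmetry and first-order autoregressive covariance structures are the three candidates.
- **Selection rule.** All "calculated models will then be compared using the Bayesian information criterion (BIC) statistic to" "select the best model in terms of covariance structure for random effects and the number of" "predictors (i.e., lowest BIC"). One criterion therefore makes both choices.
- **Outcome scale.** The change in 24-h EE is computed in "kcal as well as percent change compared to energy balance", so two outcome scales are planned.
- **Software.** "Statistical analysis will be performed using SAS with E-guide (SAS Institute, Cary, NC"). No procedure, estimation method or BIC formula is given, and no unit is fixed for aerobic capacity.
- **Reuse.** The hormone analyses later in Data Analysis use similar mixed models.
- **Contrast.** For the body-weight trajectory, the same section uses BIC only to compare two covariance structures.
- **Hypothesis at stake.** Secondary Hypothesis 3 predicts that the EE response to cool exposure varies with body adiposity. Percent body fat is the adiposity variable in the listed model.

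**The concern.** Choosing a covariance structure and choosing fixed effects are different tasks. REML likelihoods can be compared between covariance structures when the fixed effects are the same. They cannot be compared between models with different fixed effects, because the REML likelihood contains a term that depends on the scale of the predictors and of the outcome. A single lowest-BIC search over both dimensions, run under REML, would therefore let the unit of a variable decide whether it counts as a determinant of the EE response. This happens with complete data. A separate issue holds under either estimator: a predictor that carries an a priori hypothesis should not be removable by a fit statistic. What is at stake is which determinants are reported, and the p-values reported with them, in the EE-response and hormone models.

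**Working it through.** **Inputs from the plan.** 68 subjects (Sample Size Calculation, Table 2). Three intervention chamber sessions (Days 14, 18 and 21). Six listed predictors, three covariance structures, and outcomes in kcal and in percent.

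**Assumed inputs.** REML estimation, with BIC = -2RLL + (number of covariance parameters) × ln(subjects). Between- and within-subject SDs of 80 and 80 kcal. Percent body fat SD 9, aerobic capacity SD 0.5 L/min, mean EE 2200 kcal. Compound symmetry.

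**1. The plan's own figure.** The plan gives no number for the BIC step. Its n supplies the penalty, so n is checked first. By Fisher z, n = ((2.576 + 0.842)/0.4236)² + 3 = 68.07, against the stated 68. Power at n = 68 is 0.799-0.806, against 0.804 in Table 3. Both agree. The penalty is ln 68 = 4.22 per parameter. If the interim rule raises n to 124, it is ln 124 = 4.82.

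**2. The scale term.** -2RLL contains log|X'V⁻¹X|.
- Multiplying one predictor by c raises this term by exactly 2 ln c with no change in fit. Years to months: 2 ln 12 = 4.97. L to mL: 2 ln 1000 = 13.8.
- Dividing the outcome by k raises it by 2 ln k per predictor. At 2200 kcal, 1% is 22 kcal, so moving from kcal to percent shifts the comparison by about 2 ln 22 = 6.2.

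ML has no such term. These shifts do not depend on the assumed SDs, apart from the 2200 kcal behind the 6.2.

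**3. One simulated data set, age unrelated to response.** BIC change on adding age (positive means drop):

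| | days | months | years | decades |
|---|---|---|---|---|
| REML, CS | +9.62 | +2.79 | -2.18 | -6.78 |
| REML, AR1 | +9.77 | +2.93 | -2.04 | -6.64 |
| REML, DIAG | +10.22 | +3.39 | -1.58 | -6.19 |
| ML, CS | +4.21 | +4.21 | +4.21 | +4.21 |

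Under REML the same data drop age in months and keep it in years. Under ML the decision never changes.

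**4. Hand check of the retention rates.** Under compound symmetry, adding a subject-level predictor with standard deviation SD changes the REML BIC by about ln(68 × 3 × SD²/(80² + 3 × 80²)) - ln 2π - LR. Here LR is the likelihood-ratio statistic, about chi-square on 1 df for an unrelated predictor; ln 2π = 1.84; and the denominator is 25,600.
- Percent body fat, kcal outcome: ln(0.645) - 1.84 = -2.28. Already negative, so it is always kept.
- Percent body fat, percent outcome: -2.28 + 6.18 = +3.90. Kept only if LR > 3.90, about 5% of the time.
- Aerobic capacity in L/min, kcal outcome: ln(0.00199) - 1.84 = -8.06. Always kept.
- Aerobic capacity in mL/min, kcal outcome: -8.06 + 13.82 = +5.76. Kept only if LR > 5.76, about 1.6%.
- ML, any scale: kept if LR > 4.22, about 4%.

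**5. Simulation.** Unrelated predictor kept:

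| | REML BIC | ML BIC |
|---|---|---|
| Percent body fat, kcal outcome | 100% | about 2-7% |
| Percent body fat, percent outcome | about 4% | about 2-7% |
| Aerobic capacity, L/min | 100% | about 2-7% |
| Aerobic capacity, mL/min, kcal outcome | about 1% | about 2-7% |

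**6. Real predictors.** With SD pairs from 50/50 to 120/100 kcal, real aerobic capacity (r = 0.4) in mL/min is kept by REML BIC in 80-88% of trials on the kcal outcome and 44-53% on the percent outcome. In L/min it is always kept. ML BIC keeps a real predictor in 92% of trials at r = 0.4 and in 68-70% at r = 0.3, whatever the units.

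**The case against.** - **REML is not in the documents.** This is the strongest objection, and it stands. A reader might infer that the plan specifies REML and is therefore wrong as written. It names only SAS; the default estimator and the form of its BIC are assumptions here. Under ML the scale dependence vanishes. What the documents do show is a joint rule with no estimator stated.
- **The six predictors may be meant to stay.** The text first lists them as included, and BIC might govern only additions. But the rule explicitly extends to the number of predictors, and no other candidates are named for these models. The reading is open, which is itself a reason to settle it.
- **Percent versus fraction.** A reader might infer that recoding body fat as a fraction would change whether it is kept. On the kcal outcome it would not: the shift is 2 ln 100 = 9.2, but unrelated body fat is kept in 100% of trials either way. The plan also names the variable as a percentage. The reversal for body fat arises between the plan's two outcome scales.
- **Real predictors lost.** A reader might infer that REML BIC discards real effects generally. With the kcal outcome, the material loss shown is for mL/min coding, and the plan gives no unit for aerobic capacity. Keeping an unrelated but listed predictor also does little harm, since it only reproduces the full model.
- **Reach.** A reader might infer that the main result is at risk. The primary association is tested by correlation and by regression with named covariates, outside this rule.

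**Conclusion.** The concern holds in a conditional form. The joint lowest-BIC rule is the plan's own. If the models are fitted by REML, the choice of predictors depends on scale: by exactly 2 ln c for a rescaled predictor, and by about 6.2 between the plan's two outcome scales at a mean EE of 2200 kcal, against 4.2 for the usual penalty. The retention percentages are illustrative because they rest on assumed SDs, units and compound symmetry. If ML is used, only the second issue remains: BIC may still remove a predictor that carries a stated hypothesis, and at r = 0.3 it does so in about 30-32% of simulated trials. The effect is confined to the EE-determinant models and the hormone models that reuse them. The primary EE-intake association, its alpha, the sample size and the interim rule are not affected. This should be corrected, but it does not threaten the main conclusion.

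**What to change.** Replace the joint rule in Data Analysis with wording to this effect: age, sex, race, percent body fat, aerobic capacity and type of intervention stay in the model whatever the BIC; BIC from REML fits is used only to choose among DIAG, CS and AR1 with those fixed effects held constant; any comparison of predictor sets is made by ML and labelled exploratory. Apply the same rule to the hormone models. The cost is one or two sentences in the SAP, with no extra data, subjects or procedures.
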